#### **4.2 Exclusion criteria**

Subjects fulfilling any of the following criteria are not eligible for inclusion in this study. No additional exclusions may be applied by the investigator, in order to ensure that the study population will be representative of all eligible subjects.

1. Subjects with a history of hypersensitivity to any of the study drugs, including history of hypersensitivity to drugs of similar chemical classes, or allergy to ACEIs, ARBs, or NEP inhibitors as well as known or suspected contraindications to the study drugs.
2. Subjects with a history of angioedema drug related or otherwise
3. Subjects with symptomatic hypotension or systolic blood pressure  $<$ 100 mmHg at screening or  $<$ 95 mmHg at randomization.
4. Subjects with any conditions in skin or upper extremities which would limit the ability to tolerate a wrist-worn actigraphy device on the nondominant arm for 24 hours/day for the duration of the study.
5. Subjects unwilling or unable to wear and operate the study measurement devices for the phases required.
6. Subjects who are currently hospitalized, or were discharged from the hospital within 4 weeks prior to enrollment.
7. Subjects who are already taking sacubitril/valsartan
8. Subjects who are nonambulatory or use mobility assistive devices such as motorized devices, wheelchairs, or walkers. The use of canes for stability while ambulating is acceptable.
9. Subjects with physical activity impairment primarily due to conditions other than heart failure such as:
  - Exertional angina
  - inflammatory or degenerative joint disease
  - gout
  - peripheral vascular disease

- neurologic diseases affecting activity or mobility

10. Subjects with nontypical circadian behavioral patterns (for example: shift workers actively rotating shifts, subjects with non-24-hour sleep wake disorder as result of blindness)

11. Subjects with tremor, rigor or mobility limitations affecting the nondominant arm (e.g. due to Parkinson's disease, joint contractures, paralysis, injury etc.)

12. Subjects with chronic obstructive pulmonary disease (COPD) who require supplemental oxygen.

13. Subjects using a continuous positive airway pressure (CPAP) devices or similar technology for treatment of sleep disorders

14. Subjects unwilling or unable to refrain from the use of prescription and/or over the counter (OTC) sleep aids for the duration of the study

15. Subjects with body mass index (BMI) > 35

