**Table 5-4 Treatment Dose Levels during the open-label epoch**

Dose Level*	Sacubitril/valsartan
1	24/26 mg BID
2	49/51 mg BID
3	97/103 mg BID

\*sacubitril/valsartan 24/26 mg BID (Dose Level 1) will be given to subjects who completed the double-blind treatment epoch on Dose Level 1 and is also available if down-titration is required.

Open-label sacubitril/valsartan will be packaged and labeled by the sponsor in accordance with the US Code of Federal Regulation governing handling of investigational treatments, and will be dispensed by the study physician. Open-label treatment will be provided for 8 weeks.

All subjects entering the open label-treatment epoch will be given sacubitril/valsartan 49/51 mg BID (Dose Level 2) unless they completed the double-blind treatment epoch on Dose Level 1. Instead, these subjects will enter the open-label epoch on sacubitril/valsartan 24/26 mg BID dose (Dose Level 1). At each subsequent study visit during the open-label epoch, the study physician will sequentially up-titrate the study drug dose (based on clinical tolerance and the USPI) to achieve the targeted desired dose of 97/103 mg sacubitril/valsartan BID (Dose Level 3).

During the open label phase, patients not tolerating the escalation from Dose Level 1 to Dose Level 2 (or Dose Level 2 to Dose Level 3) can be titrated down to the next lower Dose Level, if, in the investigator's judgement, the adjustment/elimination of concomitant medications is not possible or does not alleviate the side effects of concern. See [Section 5.5.5](#).

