## **5.2 Treatment arms**

Subjects will be assigned at Day 1 to one of the following two treatment arms in a 1:1 ratio:

- sacubitril/valsartan; or,
- enalapril

Subjects will be assigned at Week 8 to open label extension phase during which all subjects will receive:

- sacubitril/valsartan

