- All subjects that complete the 8 week double-blind treatment epoch will proceed into the 8-week open-label epoch on sacubitriI/valsartan.
- At Week 8 (Visit 8), Drug accountability will be performed and all double-blind treatment medication will be returned to the site.

- Open-label sacubitril/valsartan will be dispensed at Week 8 (Visit 8) with subject's instructions **NOT** to start their open label-treatment until after completing a 36-hour wash out. All patients will have the wash out in order to maintain the blinding of the core study.

All dose levels will be available throughout the study. Dose adjustments to lower dose levels may be made at any time at both scheduled and unscheduled visits only if indicated for blood pressure control/tolerability reasons.

All study treatment assigned by the IRT will be recorded/databased in the IRT.

All dosages prescribed and dispensed to the subject and all dose changes during the study must be recorded in the IRT and on the Dosage Administration Record eCRF.

Study medication should be taken twice daily with a glass of water with or without food.

If the subject misses taking any study drug dose, he/she should take it as soon as possible and within 4 hours of the scheduled dose time. If the patient is unable to take the missed dose within 4 hours of the scheduled dose time, he/she should skip the missed dose and return back to his/her regular study drug administration schedule.

The investigator must promote compliance by instructing the subject to take the study treatment exactly as prescribed and by stating that compliance is necessary for the subject's safety and the validity of the study. The subject must also be instructed to contact the investigator if he/she is unable for any reason to take the study treatment as prescribed.

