### **5.5.5 Permitted dose adjustments and interruptions of study treatment**

Every attempt should be made to maintain subjects on the target study drug dose level for as long as possible throughout the study. If, however, in the opinion of the investigator, a subject is unable to tolerate the protocol-specified target dose, the investigator should consider whether dose adjustments of concomitant medications may rectify the situation before reducing the dose of study treatment. If adjustment of the concomitant medications is not possible or does not alleviate the side effects of concern, the investigator may down-titrate the dose of the study drug to the previous dose level. If needed, the study drug may be stopped completely, if this occurs, the subject should return to the clinic as soon as possible, after discontinuation of study drug, for an end of study visit. Subjects may restart their current dose of study drug following an interruption of treatment, based on investigator judgment.

Study drug dose level adjustments should be mainly based on overall safety and tolerability with special focus on:

- Hyperkalemia
- Symptomatic hypotension
- Clinically significant decrease in eGFR/increase in serum creatinine (defined as a serum creatinine of  $\geq 0.5\text{mg/dl}$  with at least a 25% decrease in eGFR).

These changes must be recorded on the Dosage Administration Record CRF.

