**5. Study drug restart after temporary treatment interruption**

- Once the investigator considers the subject's condition appropriate for receiving the study drug, the investigator should re-start the subject on study treatment at the most appropriate and allowable dose level per his/her medical judgment.
- If tolerated, the subject should be titrated up to the next dose level every 1 to 4 weeks, as per the investigator's judgment.

- In some instances, Dose Level 1 or 2 could be maintained if the investigator considers that the subject's condition would not allow any further up-titration to the target dose of study medication (Dose Level 3). In this case, it would be acceptable to maintain the subject at Dose Level 1 or 2, whichever is the higher and tolerated dose level by the subject, but reasons for not getting to Dose Level 3 need to be captured in the eCRF.
- Should the subject not tolerate the re-start study drug dose level, he/she may be down-titrated again (if appropriate) or discontinued from study treatment.

Subjects re-started on the study drug will retain their original randomization and study identification numbers.

The IRT must be contacted to register any changes in the subject's study treatment dose level, including in cases of temporary and permanent withdrawal or re-start of the study drug, and to obtain the medication numbers of the study drug supplies required for the new study treatment dose level. All dose changes and interruptions must also be recorded on the Dosage Administration Record eCRF.

Study visits should occur as close as possible to the pre-defined visit and time schedule described in [Table 6-1](#). The timeframe between the regular visits should be maintained as scheduled, irrespective of the number of unscheduled visits that may be performed in between, or dose interruptions that may occur.

In case of pregnancy discovered during the study, the patient should be instructed to stop taking the study drug immediately. (See [Sections 6.5.6](#) and [Section 7.4](#))

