### **5.6.2 Discontinuation of study treatment**

Subjects may voluntarily discontinue the study drug for any reason at any time.

Study drug must be discontinued under the following circumstances:

- Withdrawal of consent
- Pregnancy
- Use of prohibited concomitant medication
- Any protocol deviation that constitutes a risk to the subject
- Investigator believes that continuation of study drug may be detrimental to the subject's well-being
- Study medication may be discontinued at the investigator's discretion if any of the following occur:
  - Any severe suspected drug related AE
  - Suspected occurrence of angioedema. A subject with any signs or symptoms of clinically significant angioedema should be thoroughly evaluated by the investigator to determine if it constitutes a reason for discontinuation of study medication.

Depending on the serum potassium, blood pressure, or eGFR, subjects may need to have their study drug dose or the dose of another concomitant medication reduced or discontinued; or, if appropriate, have potentially contributing agents adjusted. Refer to appendices for treatment guidelines for hyperkalemia, hypotension or renal dysfunction, respectively.

In the case of study drug discontinuation, every effort must be made to complete an end of study visit and obtain follow up health status information for any subjects that withdraw from the

study. If the subject refuses, he/she should be contacted by telephone in place of protocol-specified visits unless the subject expressly refuses such contacts.

The investigator must notify the sponsor of any study drug discontinuation and record it on the Dosage Administration Record eCRF.

If discontinuation of study treatment occurs, the subject should NOT be considered withdrawn from the study. The subject should return to the clinic as soon as possible, after discontinuation of study drug, for an end of study visit. All assessments from the final visit (Visit 13) in the visit schedule of assessments ([Table 6-1](#)) must be completed and recorded in the eCRF. The Study Completion eCRF will also need to be completed. The investigator must determine the primary reason for the subject's premature discontinuation of study treatment and record this information in the eCRF.

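### Any past angioedema bars entry, yet clinically significant angioedema on study does not by itself stop study drug or block open-label sacubitril/valsartan

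*Protocol*

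**What the plan says.** - **Entry.** Protocol 4.2, criterion 2, excludes "Subjects with a history of angioedema drug related or otherwise". Section 6 has eligibility confirmed before study treatment starts and states no re-check at Week 8.
- **Stopping.** Protocol 5.6.2 says "Study medication may be discontinued at the investigator's discretion if any of the following occur", and suspected angioedema is one of the two events that follow. A patient with clinically significant signs or symptoms "should be thoroughly evaluated by the investigator to determine if it constitutes a reason for discontinuation of study medication". The same section makes stopping mandatory when the investigator thinks that continuing could harm the patient.
- **Restart.** Protocol 5.5.5 says "Subjects may restart their current dose of study drug following an interruption of treatment, based on investigator judgment". Its step 5 adds "Once the investigator considers the subject's condition appropriate for receiving the study drug, the investigator should re-start the subject on study treatment". Neither makes an exception for angioedema.
- **Rollover.** Protocol 5.2 says "Subjects will be assigned at Week 8 to open label extension phase during which all subjects will receive" sacubitril/valsartan, and 5.5.4 says "All subjects that complete the 8 week double-blind treatment epoch will proceed into the 8-week open-label epoch". Under 5.1.1 patients start open-label drug at Dose Level 2 "unless they completed the double-blind treatment epoch on Dose Level 1". No other condition on open-label entry is visible.
- **SAP.** Section 2.3.1 lists angioedema among the reasons for not reaching Dose Level 3. Section 2.8.4.3 tabulates whether study drug was discontinued because of the angioedema event and allows the answer no. Continued dosing after an event is therefore foreseen.

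**The concern.** The entry criterion treats angioedema of any cause, at any past time, as reason enough to keep a patient off both drugs. A patient who has an event after randomization now has that same history, but the protocol attaches no fixed consequence to it.

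Section 3.6 says sacubitril/valsartan may cause angioedema. Section 6.5.4 implicates inhibition of both ACE and NEP, calls the effect potentially dangerous and mentions airway compromise in severe cases. Two situations follow. After an event on blinded enalapril, rollover at Visit 8 would be the first exposure to sacubitril/valsartan. After an event on blinded sacubitril/valsartan, rollover would continue it. The 36-hour washout addresses overlap of the two drugs, not a previous event. Adjudication (8.5) assigns severity but triggers no treatment action.

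What is at stake is the safety of a very small number of patients. The primary comparison is not in question.

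**Working it through.** The documents state no figure on this point to reproduce. The check is a reading of the rules in sequence, followed by simple bounds.

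**1. Path of one patient with clinically significant angioedema.**
- The required evaluation takes place (5.6.2).
- If the investigator believes that continuing may be detrimental, the stop is mandatory. The patient goes to an end-of-study visit and is not a double-blind completer, so there is no gap on this branch.
- If the investigator does not believe so, stopping is optional. The patient may continue, or interrupt and restart under 5.5.5.
- If that patient completes Week 8, 5.2 and 5.5.4 lead to open-label sacubitril/valsartan, with only the dose level conditional.

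The gap is confined to the last two steps.

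**2. Do other provisions close it?** The medical monitor is notified (6.5.4). Angioedema is assessed at every office visit, including Visit 8, and a report at a tele-visit prompts a request for an unscheduled visit (Table 6-1 and its footnote 8). An emergency code break is available when safe treatment requires it (5.5.9). Each makes further exposure less likely, but none prohibits it.

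**3. Maximum further dosing (days from Table 6-1).**
- Event at Week 2 (Day 14): 56 − 14 = 42 blinded days, plus 112 − 56 = 56 open-label days, 98 in total, less the 36-hour washout.
- Event at Visit 8 (Day 56): 112 − 56 = 56 days, less the washout.
- Event at Week 9 (Day 63): 112 − 63 = 49 days.

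These are worst-case maxima. They assume that every decision goes towards continuing.

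**4. Expected number newly exposed at Visit 8.** The enalapril arm has 68 patients (Table 5-1) and the planned drop-out is 20% (9.8), so 68 × 0.8 = 54.4, about 54 completers. The 8-week event rate *p* and the 90% share stopped by existing controls are assumptions. Expected patients = 54*p*, and the chance of at least one = 1 − (1 − *p*)^54. With 90% stopped, *p* is replaced by *p*/10.

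| Assumed *p* | Nobody stopped | 90% stopped |
|---|---|---|
| 0.1% | 0.054 patients, 5.3% | 0.0054 patients, 0.5% |
| 0.5% | 0.27 patients, 23.7% | 0.027 patients, 2.7% |
| 1% | 0.54 patients, 41.9% | 0.054 patients, 5.3% |

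**5. Statistical cost of stopping one patient.**
- Open-label paired tests: √(54/53) − 1 = 0.9%. With 10% also non-evaluable, 68 × 0.7 = 47.6, about 48, and √(48/47) − 1 = 1.1%.
- Primary analysis: the evaluable number is 136 × 0.7 = 95 to 136 × 0.8 × 0.9 = 98. One patient stopped before Week 8, with Week 1 carried forward under 9.4.3, is about 1% of it.

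**The case against.** The strongest reply is that the matter is already handled by clinical judgment, and that discretion is a legitimate design choice. The evaluation comes first and the stop for detriment is mandatory. The protocol also leaves other serious events to judgment: severe suspected drug-related adverse events (5.6.2), acute kidney injury (Appendix 3) and adverse events suggesting liver toxicity (Appendix 2). Its fixed stops, such as pregnancy, prohibited medication and potential Hy's Law cases, rest on tests, records or laboratory thresholds. All of this stands, so a reader should not infer that angioedema is singled out for weaker handling. It does not remove the mismatch with the protocol's own entry rule.

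A second reply is that any new trigger still depends on someone judging the event clinically significant. That also stands. A reader might infer that a fixed rule gives every site the same protection. It does not: sites may still classify events differently, and only the consequence after classification becomes fixed.

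A third is over-reach, since the SAP's list of potential causes includes food, insect bites and pollen. This is weak, because exclusion 2 already ignores cause.

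A reader might also see significance in where the discretionary item sits within the 5.6.2 list. Its wording is plainly permissive, and the layout may be an artefact of PDF extraction, so nothing should rest on that.

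**Conclusion.** The point holds in a limited form. After clinically significant angioedema, if the investigator judges continuation not detrimental, the visible text permits continued dosing or restart. On completion of Week 8 it sends the patient to open-label sacubitril/valsartan. Existing controls make this unlikely without prohibiting it.

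Two stronger readings are not supported. A reader might infer that continued or first exposure is what normally follows an event, or that 98 days is an expected exposure. The evaluation and the mandatory stop for detriment come before any continuation, so 98 days is only a ceiling. A reader might also infer that blinded staff could never learn which drug was involved, but 5.5.9 allows an emergency code break.

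The expected count is small: 0.005 to 0.05 patients newly exposed with existing controls, or at most 0.05 to 0.54 if nobody were stopped. Every count rests on assumed rates, and the 90% share is also assumed. The conclusion concerns visible text only. The US prescribing information is not in the documents and some appendices are redacted, although the cross-reference in 5.6.2 names only hyperkalemia, hypotension and renal dysfunction. The change is recommended because the event is serious and the remedy is cheap. Power and the primary comparison are not materially affected.

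**What to change.** Amend four places in the protocol:

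- **5.6.2.** Add to the mandatory stops: clinically significant angioedema, as judged by the investigator after the required evaluation and in consultation with the medical monitor, in either arm and either epoch. The stop is permanent and does not wait for adjudication. Avoid the word confirmed, which 8.5 ties to the adjudication committee. Suspected events stay under the present evaluation.
- **5.5.5.** Exclude these patients from the restart provisions.
- **5.2 and 5.5.4.** State that these patients do not enter the open-label epoch, and that open-label drug is not dispensed while a suspected event is unresolved at Visit 8.

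Stopped patients complete the Visit 13 assessments, as 5.6.2 already provides. A patient held at Visit 8 keeps the calendar visits, as 5.5.5 already requires for interruptions. The rule is the same in both arms, so it requires no unblinding, and the SAP needs no change.

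The cost is one amendment with IRB/IEC approval (11.1) and about 0 to 1 patient lost from the analyses. A held patient may need one extra dispensing contact, and that patient's Week 9 actigraphy would cover less time on open-label drug. No new data are collected.

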**Table 5-6      Study drug dispensed during open-label treatment epoch**

Visit	Dose Level	Sacubitril/ valsartan**	Route	Timing
Week 8/Visit 8	1	24/26 mg	Oral	AM & PM
Weeks 10-16	2	49/51 mg	Oral	AM & PM
	3	97/103 mg	Oral	AM & PM

\*\*Investigational product labeling for sacubitril/valsartan dose levels is based on the total contribution of both components of sacubitril/valsartan and reads, 50 mg, 100 mg and 200 mg. This is equivalent to the sacubitril/valsartan dose levels 24/26 mg, 49/51 mg and 97/103 mg, respectively.

- All subjects entering the open-label treatment epoch will start open-label treatment on sacubitril/valsartan 49/51 mg BID (Dose Level 2) unless they completed the double-blind treatment epoch on Dose Level 1. Instead, these subjects will enter the open-label epoch on sacubitril/valsartan 24/26 mg BID dose (Dose Level 1).
- Study treatment will be force-titrated every 2 weeks to reach the target dose of sacubitril/valsartan 97/103 mg BID (Dose Level 3).

Schedule and dose adjustments will only be allowed if, in the investigator's judgement, the adjustment/elimination of concomitant medications is not possible or does not alleviate the side effects of concern. See [Section 5.5.5](#).

### **5.5.5 Permitted dose adjustments and interruptions of study treatment**

Every attempt should be made to maintain subjects on the target study drug dose level for as long as possible throughout the study. If, however, in the opinion of the investigator, a subject is unable to tolerate the protocol-specified target dose, the investigator should consider whether dose adjustments of concomitant medications may rectify the situation before reducing the dose of study treatment. If adjustment of the concomitant medications is not possible or does not alleviate the side effects of concern, the investigator may down-titrate the dose of the study drug to the previous dose level. If needed, the study drug may be stopped completely, if this occurs, the subject should return to the clinic as soon as possible, after discontinuation of study drug, for an end of study visit. Subjects may restart their current dose of study drug following an interruption of treatment, based on investigator judgment.

Study drug dose level adjustments should be mainly based on overall safety and tolerability with special focus on:

- Hyperkalemia
- Symptomatic hypotension
- Clinically significant decrease in eGFR/increase in serum creatinine (defined as a serum creatinine of  $\geq 0.5\text{mg/dl}$  with at least a 25% decrease in eGFR).

These changes must be recorded on the Dosage Administration Record CRF.

